6.1 Activities/Assessments and Associated Endpoints

6.1.1 In-Lab Gait, Strength, and Functional Assessments

3D Motion Capture Assessment

Participants will perform specific tasks while being monitored with a 3D motion capture system, wrist and lumbar wearable sensors, and surface electromyography (EMG) sensors. For 3D tracking, small plastic lightweight markers will be placed (14 mm in diameter) on the legs and trunk. These markers are covered in retro-reflective tape and can be detected by the optical motion capture cameras. Surface electromyography (EMG) sensors will be placed on vastus lateralis, vastus medialis, medial hamstrings, lateral hamstrings, medial gastrocnemius, and lateral gastrocnemius muscles after cleaning and shaving the skin. The tasks to be performed include (a) walking at self-selected speed (4-12 trials), (b) walking at fast speed (4-12 trials), (c) sit to stand (4 trials), and (d) standing with eyes open and eyes closed (two 30 second trials in each condition). Practice trials are performed prior to each task.

Devices to be used: Qualisys cameras, Sony video camera, AMTI force plate, AMTI staircase, Delsys EMG

Raw Data obtained:

- Ground reaction force (x, y, z)
- Marker trajectories (x, y, z)
- Raw electromyogram (various muscles – VM, VL, MH, LH, MG, LG)

Derived measures:

Gait Measures
Cadence (steps/min)
Step length symmetry
Gait speed (m/s)
Stride duration (s)
Stride duration asymmetry (s)
Step duration (s)
Step duration asymmetry (s)
Initial double support time (s)
Terminal double support time(s)
Total double support time (s)
Single limb support time (s)
Stance time (s)
Swing time (s)
Step length (m)
Peak knee index (%BodyWeight x Height)
Knee flexion excursion (deg)
Knee extension excursion (deg)
Peak medial quadriceps-medial hamstrings co-contraction during loading response during walking at self-selected pace
Peak lateral quadriceps-lateral hamstrings co-contraction during loading response during walking at self-selected pace
Peak sagittal trunk angle (deg)
Peak knee adduction moment (%BodyWeight x Height)
Peak knee flexion moment (%BodyWeight x Height)
Knee adduction moment impulse (%BodyWeight x Height x Sec)
Knee flexion moment impulse (%BodyWeight x Height x Sec)
Peak sagittal total support moment (%BodyWeight x Height)
Sit-to-stand measures

Number of sit-to-stands
Duration (s)
Maximum acceleration (m/s ²)
Minimum acceleration (m/s ²)
Peak total sagittal lower extremity support moment (%Bodyweight*Height)

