7. ANALYSIS PLAN

7.1. Analysis of Primary Aim and Endpoints

Details of the analysis of this study will be documented in the Statistical Analysis Plan (SAP). The analyses described in the approved SAP will be followed if different from what is described in this protocol.

Primary Aim: Measure the effect of PT on functional performance using digital measures from wearable sensors.

The following analyses will be performed to address this primary aim.

A. Validate wearable sensor-based metrics of functional biomechanical tests in people with knee OA against optical motion capture

Data from the lumbar sensor and optical motion capture during gait and sit-to-stand tasks during in-lab visits will be used for this analysis. Wearable sensor metrics will be compared against gold standard metrics from the optical motion capture system using intra-class correlation coefficient (ICC) and its 95% lower and upper confidence limits. The ICC reflects both the degree of correlation and agreement between the measurements. We will interpret agreement between measurements according to the following benchmarks: $ICC \leq 0.4$ indicates 'poor', 0.4 to 0.59 'moderate', 0.6 to 0.74 'good', and 0.75 to 1 'excellent' reliability (Cicchetti et al., 1994). In addition, we will also compute the mean, variance and percentage error between the standard and the digital measurements. Bland–Altman plots and 95% limits of agreement (average difference ± 1.96 standard deviation of the difference) will also be computed.

B. Compare wearable sensor-based metrics of physical performance in people with knee OA with standardized physical performance outcomes.

Wearable sensors with excellent reliability from analysis A will be examined. Sensor-based metrics from lumbar sensor during physical performance tests in-lab will be correlated with standardized physical performance outcomes using Pearson's product-moment correlations or Spearman's rank order correlations depending on their normality.

C. Assess the effects of exercise-based PT on outcomes from wearable sensors during in-lab physical performance tests

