### 3. OUTCOMES AND ANALYSES

#### Terminology

Digital metrics = data from wearable sensors including lumbar and wrist-worn sensors

Physical Function = overall term that includes assessments of physical performance, functional biomechanical tests, and at home physical activities.

Physical performance tests = standardized tests including 5 times sit-to-stand test, 15 second step-up test, stair climbing test, 6 minute walk test, and SPPB

Functional biomechanical tests = activities assessed using optical motion capture including walking, fast walking, stair ascent and descent, sit to stand, and balance

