## B. In-lab Data Sit-to-stand Measures

**Table 2. Sit-to-stand measures derived from Sit2StandPy algorithm applied on the lumbar sensor and from Optical Motion Capture System**

	Sit2StandPy applied on Lumbar Sensor	Optical Motion Capture System
a.	Number of sit-to-stands	Number of sit-to-stands
b.	Duration (s)	Duration (s)
c.	Maximum acceleration (m/s  )	Maximum acceleration (m/s  )
d.	Minimum acceleration (m/s  )	Minimum acceleration (m/s  )
e.	SPARC: SPectral ARC length	
f.		Peak total sagittal lower extremity support moment (%Bodyweight*Height)

g.		Peak sagittal trunk angle (deg)
h.		Peak medial quadriceps-medial hamstrings co-contraction
i.		Peak knee adduction moment (%BodyWeight x Height)
j.		Peak knee flexion moment (%BodyWeight x Height)
k.		Peak knee flexion (deg)

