**E. At-home Data: Gait, sit-to-stand and physical activity measures**

- Gait measures derived from GaitPy algorithm applied on the lumbar sensor
  - # of gait bouts
  - Cadence (steps/min)
  - Step length symmetry
  - Gait speed (m/s)
  - Stride duration (s)
  - Stride duration asymmetry (s)
  - Step duration (s)
  - Step duration asymmetry (s)
  - Initial double support time (s)
  - Terminal double support time(s)

- Total double support time (s)
- Single limb support time (s)
- Stance time (s)
- Swing time (s)
- Step length (m)
- Sit-to-stand measures derived from Sit2StandPy algorithm applied on the lumbar sensor
  - Number of sit-to-stands
  - Duration (s)
  - Maximum acceleration (m/s)
  - Minimum acceleration (m/s)
  - SPARC : SPectral ARC length
- Physical Activity measures based on Actigraph's Algotihms
  - Steps/day
  - Time spent in moderate and vigorous physical activity (MVPA) (min)
  - % wear-time in MVPA
  - Sedentary time (min)
  - % wear-time sedentary

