#### 4.2. Analysis of Primary Endpoints

Below is a description of the analyses performed to address the study objectives and to analyze the corresponding endpoints.

*Measure the effect of PT on physical function using digital measures from wearable sensors*

The following analyses will be performed to address this primary aim.

- A. Validate wearable sensor-based metrics of functional biomechanical tests in people with knee OA against optical motion capture

Wearable sensor metrics (Gait: Table 1 rows *a.* – *n.*; Sit-to-stand: Table 2 rows *a.* – *d.*) will be compared against the same measures obtained from the optical motion capture system (used as the gold-standard) using intra-class correlation coefficient (ICC) and its 95% lower and upper confidence limits. The ICC reflects both the degree of correlation and agreement between the measurements. We will interpret agreement between measurements according to the following benchmarks:  $ICC \leq 0.4$  indicates ‘poor’, 0.4 to 0.59 ‘moderate’, 0.6 to 0.74 ‘good’, and 0.75 to 1 ‘excellent’ reliability. In addition, we will also compute the mean, variance and percentage error between the standard and the digital measurements. Bland–Altman plots and 95% limits of agreement (average difference  $\pm 1.96$  standard deviation of the difference) will also be computed.

- B. Compare wearable sensor-based metrics of physical performance in people with knee OA with standardized physical performance outcomes.

Wearable sensors metrics showing excellent reliability from analysis A will be examined (i.e. a subset of the metrics shown in Table 1 rows *a.* – *n.* for Gait; and Table 2 rows *a.* – *d.* for Sit-to-stand). Sensor-based metrics will be derived during physical performance tests conducted in-lab and will be correlated with the corresponding standardized physical performance outcomes using Pearson’s product-moment correlations or Spearman’s rank order correlations depending on their normality.

Specifically, the comparisons that will be computed are shown in Table 5.

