Sensitivity analyses will include (a) only in participants who attended at least 80% (14 visits) of the PT visits, and (b) in all participants stratified into < 6 PT visits attended, 6-12 PT visits attended, and >12 PT visits attended.

D. Assess the effects of exercise-based PT on outcomes from wearable sensors collected at-home

The following definitions will be used for analysis of at home sensor data. Based on the literature, a recording day will be considered valid and included in the analysis if it contains at least 10 waking hours (identified using the Cole-Kripke algorithm implemented in ActiLife software) of wear-time. At-home wrist and lumbar sensor data will be summarized on a weekly basis. A week of recording will be included in the analysis if there is at least 4 valid days (as described above) in a 7-day period.

A subset of wearable sensor metrics for gait and sit-to-stand from Section 3.1. E. that are shown to have excellent reliability from analysis A, and the physical activity measures from Actigraph (Section 3.1. E) will be examined. Since *number of gait bouts* derived from free living data is not assessed in

the lab, this will be automatically included in this analysis. The same MMRM approach and sensitivity analyses described above will be used to investigate change from baseline to 6- and 12-weeks with PT on at home sensor endpoints. Mean/median for each endpoint (depending on the distribution of the endpoint) across a valid period will be used in the analyses.

E. Assess the effects of exercise-based PT in-lab tests of physical performance.

The same MMRM approach and sensitivity analyses described above will be used to investigate change from baseline to 6- and 12-weeks with PT on all physical performance outcomes described in Section 3.1. D.

F. Assess the effects of exercise-based PT using joint mechanics during in-lab functional biomechanical tests

The same MMRM approach and sensitivity analyses described above will be used to investigate change from baseline to 6- and 12-weeks with PT on all endpoints derived from optical motion capture system (Gait: Table 1. Column 2; Sit-to-stand: Table 2. Column 2; Section 3.1. C) during in-lab visits.

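### The ICC >= 0.75 gate cannot pass the at-home number of sit-to-stands when the lab script is followed, and SPARC is listed as primary but enters no primary-aim analysis

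*SAP*

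**What the plan says.** SAP 3.1 E lists 25 at-home primary endpoints, five of them sit-to-stand measures from the lumbar sensor. These include the number of sit-to-stands and "SPARC : SPectral ARC length". Both also appear as in-lab primary endpoints in SAP 3.1 B, Table 2 (rows a and e). The optical column of row e, "SPARC: SPectral ARC length", is blank.

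In SAP 4.2 A, the sensor metrics in Table 1 rows a to n and Table 2 rows a to d "will be compared against the same measures obtained from the optical motion capture system (used as the gold-standard) using intra-class correlation coefficient (ICC"), and 0.75 to 1 is called excellent. The section also promises that "we will also compute the mean, variance and percentage error between the standard and the digital measurements", but ties no pass rule to those error measures. SAP 4.2 D then takes forward only "A subset of wearable sensor metrics for gait and sit-to-stand from Section 3.1. E. that are shown to have excellent reliability from analysis A". One lumbar metric is exempt, the number of gait bouts, because it is not assessed in the lab.

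Analysis A concerns functional biomechanical tests. SAP section 3 defines these separately from the physical performance tests: "Functional biomechanical tests = activities assessed using optical motion capture including walking, fast walking, stair ascent and descent, sit to stand, and balance". Protocol 7.1 A agrees on the data source: "Data from the lumbar sensor and optical motion capture during gait and sit-to-stand tasks during in-lab visits will be used for this analysis". Protocol 6.1.1 scripts the motion-capture task as "c) sit to stand (4 trials").

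**The concern.** An ICC measures agreement relative to the spread between people. A task that gives everyone the same number of stands removes that spread, so the ICC says nothing about whether the sensor counts correctly. The SAP has no rule for an ICC that cannot be estimated. The gait-bouts exemption does not cover this count either, because a scripted count is assessed in the lab.

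For SPARC the gate works as written. The fault is that the endpoint list and the analyses do not match.

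The loss carries further. Secondary Aims 1 and 3 and Exploratory Aim 1 reuse the ICC subset or the output of 4.2 D (SAP 3.2, 3.3, 4.3 and 4.4). If the team settles the matter after seeing data, that is a post hoc choice about which primary endpoints are analysed.

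**Working it through.** The plan gives no figure of its own for this point beyond the 0.75 threshold.

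**Inputs from the documents:** 60 participants (Protocol 1.1); 4 motion-capture sit-to-stand trials (Protocol 6.1.1); ICC of at least 0.75 (SAP 3.2 and 4.2 A).

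**Assumptions, not in the documents:** ICC(2,1), absolute agreement (the SAP does not name the form); one total per participant; one stand per trial; each stand missed independently; no false detections; off-script participants differ by one stand.

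**Step 1, the algebra.** For two methods and n participants,

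ICC(2,1) = (MSR - MSE) / (MSR + MSE + 2(MSC - MSE)/n),

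where MSR, MSC and MSE are the mean squares for participants, methods and residual. Let the optical count be a constant c and the sensor count be s_i, with mean s̄.

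- SSR = 2 × Σ[(s_i - s̄)/2]² = Σ(s_i - s̄)²/2.
- SSE = Σ(s_i - s̄)²/2, because the difference s_i - c varies only through s_i.
- Both have n - 1 degrees of freedom, so MSR = MSE and the numerator is 0.

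An imperfect sensor therefore has ICC = 0. A perfect sensor has all three mean squares equal to 0, giving 0/0. This holds for any fixed count, so it does not depend on how many stands make up a trial. If even one person departs from the script, a perfect sensor has MSE = MSC = 0 and MSR > 0, so the ICC jumps from undefined to 1.

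**Step 2, how often the count passes.** Simulated chance of ICC >= 0.75, n = 60, 10,000 datasets per cell:

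| People one stand over | 0.5% misses | 1% | 2% | 5% |
|---|---|---|---|---|
| 0 | 0% | 0% | 0% | 0% |
| 1 | 29% | 9% | 1% | about 0% |
| 2 | 65% | 29% | 4% | about 0% |
| 3 | 85% | 52% | 12% | about 0% |
| 6 | 96% | 75% | 26% | about 0% |

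The row for 3 people is inflated by datasets that land exactly on 0.75. With 6 people one stand short instead, the rates are 97, 81, 35 and 0.4%.

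The visit descriptions list motion capture at baseline, week 12 and week 18, so pooling gives 60 × 3 = 180 records. Treated as independent, these still pass 0% of the time with nobody off script. With 9 of 180 one stand over, they pass 82, 25, 0.3 and 0% of the time.

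**Step 3, tracing SPARC.**

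- A, B and C stop at Table 2 row d.
- D requires an ICC from A.
- E covers the physical performance outcomes.
- F covers the optical column.

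SPARC (row e) is in none of them. Only the substudy analyses it (Table 4 and SAP 4.5).

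**Step 4, the count of endpoints.** SAP 3.1 E has 15 gait + 5 sit-to-stand + 5 activity = 25. Removing two leaves at most 23, and 3 of the 5 sit-to-stand measures.

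**Step 5, an example replacement rule.** Suppose the sensor total must equal the optical total in at least 90% of participants (54 of 60). With everyone on script and 4 stands, each participant matches with probability (1 - m)⁴, where m is the miss rate: 0.961, 0.922 and 0.815 at 1, 2 and 5% misses. The exact binomial chance of passing is 99%, 82% and about 5%. The result now follows accuracy. A per-trial version (216 of 240 trials) would pass over 99.9% of the time at all three rates, so it does not discriminate.

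**The case against.** The strongest objection is that the motion-capture task may not be the only source of counts. The Protocol's Schedule of Activities marks the modified SPPB with the symbol for optical markers, and the SPPB includes a single chair stand and two sets of five. If records of 4, 1, 5 and 5 stands were pooled with everyone on script, the median ICC would be 0.993 at 1% misses and 0.959 at 5%, and the count would always pass. The documents do conflict on this. But SAP section 3 separates the SPPB from the tests that analysis A validates, and the Protocol's visit text does not list optical capture for the SPPB. A pass obtained that way would also come from differences between tasks, not from counting accuracy, so it does not rescue the gate.

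Second, for a perfect sensor the ICC is undefined rather than low, and the planned percentage error and Bland-Altman limits would show perfect agreement. That is true, but no decision rule is attached to either, and an undefined ICC does not show excellent reliability.

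Third, the miss rates and off-script numbers are assumed. This stands for every row of the table except the first: the 0% on-script result depends on neither.

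Fourth, SAP 3.1 may be read as a list of candidates that section 4 filters, so an untested SPARC would be expected. Other metrics, however, can pass the filter; SPARC cannot, because no ICC is ever computed for it. General descriptive summaries under SAP 4.1 could still show it.

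**Conclusion.** The concern holds. When the lab script is followed, the number of sit-to-stands cannot meet the gate at any counting accuracy, and SPARC has no route into a primary-aim analysis. The first statement rests on analysis A using the scripted motion-capture task, as the SAP's terminology indicates, and on the count being fixed. If participants depart from the script, the count is not certain to be dropped, but the result then depends partly on how many do so. The SPARC statement needs no assumption.

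The effect is limited to two of the 25 at-home endpoints and the aims that reuse them. Sit-to-stand duration, both accelerations, and the gait and activity measures can still enter, and their estimates do not change. This should be corrected before analysis, though it does not threaten the study as a whole.

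**What to change.** - **SAP 4.2 A:** replace the ICC gate for Table 2 row a with a count-agreement rule fixed before data are seen. An example is sensor total equal to optical total at baseline in at least 90% of participants. The 90% is illustrative; what matters is that the rule is prespecified. State the task, the unit of record and the denominator, because a baseline held at home has no motion capture.
- **SAP 4.2 D:** admit the at-home count on that rule, not automatically. Note that scripted stands do not test false detections in daily life.
- **Table 5 and analysis C:** state that row a is not used, since the repeated chair-stand test fixes it at 5.
- **Analysis F:** exclude the optical count, since the script fixes it at 4.
- **SPARC:** either relabel it exploratory in SAP 3.1, or admit it to 4.2 D marked as not validated against optical capture.
- **SAP 3.2 and 3.3:** apply the same list wherever the ICC subset is reused.

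The cost is SAP wording and up to two more tests in the at-home false discovery rate family. No new data are needed.

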#### 4.3. Analysis of Secondary Endpoint(s)

##### **Secondary Aim 1: Compare in-lab and real world (at-home) sensor metrics with ePRO outcomes**

A. Compare change in in-lab wearable sensor metrics with ePRO outcomes

The change from baseline in ePRO measures from Section 3.2 will be calculated using the same MMRM approach detailed in Section 4.2 C. ePRO measures that show a significant change from baseline to 12-weeks will be examined for this analysis.

Wearable sensor metrics showing a significant change from baseline to 12-weeks during in-lab physical performance tests will be examined (this is the outcome of analysis performed in Section 4.2. C).

The change from baseline to week 12 in these metrics will be correlated with change from baseline in ePRO outcomes using Pearson's product-moment correlations or Spearman's rank order correlations depending on their normality.

Sensitivity analyses will be conducted to estimate the correlation between wearable sensor metrics and ePRO outcomes in (a) responders and (b) non-responders. Responders are defined as participants with  $\geq 50\%$  reduction in KOOS-derived WOMAC 3.0 pain score.

B. Compare change in at-home wearable sensor metrics with ePRO outcomes

ePRO measures from Section 3.2 that show a significant change from baseline to 12-weeks will be examined (as determined by analyses in Section 4.3 A). Wearable sensors metrics which show a significant change from baseline to week 12 during at-home wear will be examined (the outcome of analysis performed in Section 4.2. D).

Change from baseline to week 12 in these sensor metrics will be correlated with change in ePRO outcomes using Pearson's product-moment correlations or Spearman's rank order correlations depending on their normality.

Sensitivity analyses will be conducted to estimate the correlation between wearable sensor metrics and ePRO outcomes in (a) responders and (b) non-responders. Responders are defined as participants with  $\geq 50\%$  reduction in KOOS-derived WOMAC 3.0 pain score.

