7.2. Analysis of Secondary Aims and Endpoints

1. Compare in-lab and ambulatory (at-home) sensor metrics with ePRO outcomes

A. Compare change in in-lab wearable sensor metrics with ePRO outcomes

Wearable sensor metrics with excellent reliability from analysis A in Aim 1 and which show a significant change from baseline to 12-weeks during in-lab physical performance tests will be examined; ePRO measures from KOOS-derived WOMAC 3.0, KOOS, NRSna, PGA-OA that show a significant change from baseline to 12-weeks will be examined. Change from baseline to week 12 in sensor-based metrics from lumbar sensor during in-lab physical performance tests will be correlated with change in ePRO outcomes using Pearson's product-moment correlations or Spearman's rank order correlations depending on their normality.

B. Compare change in at-home wearable sensor metrics with ePRO outcomes

Wearable sensors metrics with excellent reliability from analysis A in Aim 1 and which show a significant change from baseline to 12-weeks during at-home wear will be examined; ePRO measures from KOOS-derived WOMAC 3.0, KOOS, NRSna, PGA-OA that show a significant change from baseline to 12-weeks will be examined. Change from baseline to week 12 in sensor-based metrics from lumbar sensor during at-home periods will be correlated with change in ePRO outcomes using Pearson's product-moment correlations or Spearman's rank order correlations depending on their normality.

2. Assess the effect of physical therapy on sleep using ePRO (DSIS questionnaire) and wearable sensor metrics

The same MMRM approach and sensitivity analyses described above will be used to investigate change from baseline to 6- and 12-weeks with PT on sleep outcomes.

3. Assess the persistence of the physical therapy effect from week 12 to week 18 using in-lab and ambulatory (at-home) sensor metrics, and ePROs

In-clinic and at-home endpoints that showed a significant change from baseline to week 12 will be examined. Similar MMRM approach to that described above will be used to investigate change in outcomes from baseline to 18-week

timepoints. The outcome measures will be expressed as the change from baseline at each visit (i.e. 6, 12 and 18 weeks). We compare the effects at week 12 and week 18 by using linear contrasts.

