### 3.2. Secondary Endpoints

*Secondary Aim 1: Compare in-lab and real world (at-home) sensor metrics with ePRO outcomes*  
*Time period: Change from baseline to week 12.*

**Wearable sensor metrics** from 3.1 A (Table 1 Column 1); 3.1 B (Table 2 Column 1) and 3.1 E. As described in the analysis Section 4 below, only a subset of these endpoints that show excellent agreement with the gold standard measures during in-lab assessments (ICC >= 0.75) will be investigated for this aim.

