#### Electronic patient reported outcome (ePRO) endpoints

- KOOS-derived WOMAC 3.0 Pain score
- KOOS-derived WOMAC 3.0 Function score
- Numeric Rating Scale for pain during nominated activity (NRSna)
- Patient Global Assessment of Osteoarthritis (PGA-OA)
- KOOS-derived WOMAC 3.0 stiffness
- KOOS Pain
- KOOS Symptoms
- KOOS ADL
- KOOS Sports/Rec
- KOOS QOL

*Secondary Aim 2: Assess the effect of PT on sleep using ePRO (DSIS questionnaire) and wearable sensor metrics*

*Time period: change from baseline to week 12*

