## 4. ANALYSES AND SUMMARIES

### 4.1. General Methods

Data will be summarized using descriptive statistics (number of subjects (n), mean, median, standard deviation, minimum and maximum) for continuous (or near continuous) variables, and using frequency and percentages for discrete variables. Shapiro-Wilk test will be used to assess normality of variables. Non-parametric statistical methods will be used to analyze non-normally distributed variables.

P-values will be generated where appropriate and any p-value < 0.05 will be considered statistically significant. If multiple p-values are generated within an analyses, Benjamini-Hochberg false discovery rate (FDR) correction will be used to determine significance. P-values will be rounded to 3

decimal places and therefore presented as 0.xxx; P-values smaller than 0.001 will be reported as ‘<0.001’.

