### **Secondary Aim 3: Assess the persistence of the PT effect from week 12 to week 18 using in-lab and real world (at-home) sensor metrics, and ePROs**

In-clinic and at-home endpoints that show a significant change from baseline to week 12 will be examined (output of analyses 4.2. C. and D.). ePRO measures from Section 3.2 that show a significant change from baseline to 12-weeks will be examined (as determined by analyses in Section 4.3. A). Similar MMRM approach to that described above will be used to investigate change in these outcome measures from baseline to 18-week timepoints. The outcome measures will be expressed as the change from baseline at each visit (i.e. 6, 12 and 18 weeks). We will compare the effects at week 12 to week 18 by using linear contrasts.

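### Secondary Aim 1's responder split is made on one of the correlated outcomes, so it is not a sensitivity analysis; a lesser point is that the week-12 gate tilts Secondary Aim 3 toward apparent loss for weak endpoints

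*SAP*

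**What the plan says.** **Secondary Aim 1 (SAP 4.3, parts A and B).** Change in sensor metrics is correlated with change in ePROs, by Pearson or Spearman. Both parts then add: "Sensitivity analyses will be conducted to estimate the correlation between wearable sensor metrics and ePRO outcomes in (a) responders and (b) non-responders". Responders are participants with at least a 50% "reduction in KOOS-derived WOMAC 3.0 pain score". The ePRO list in SAP 3.2 has ten entries, and the first is "KOOS-derived WOMAC 3.0 Pain score". The same section fixes the window ("Time period: Change from baseline to week 12"), so the visit is not in doubt. Protocol 7.2 has the correlations but not the responder split. The SAP gives no reason for the split, no expected responder share, no rule for reading the results and no correction for restricted range.

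**Secondary Aim 3 (SAP 4.3).** The gate is: "In-clinic and at-home endpoints that show a significant change from baseline to week 12 will be examined". ePROs face the same gate. Then: "We will compare the effects at week 12 to week 18 by using linear contrasts". Protocol 7.2, aim 3, has the matching gate: "In-clinic and at-home endpoints that showed a significant change from baseline to week 12 will be examined". SAP 4.1 can make it stricter than p<0.05: "If multiple p-values are generated within an analyses, Benjamini-Hochberg false discovery rate (FDR) correction will be used to determine significance".

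**The concern.** A sensitivity analysis asks the same question under different assumptions. A correlation computed after cutting the sample on one of the two correlated variables asks a different question. For WOMAC pain, and usually for close pain scores when the sensor tracks pain, each stratum has less spread in pain change, so its correlation generally drops although the relation is the same in everyone. For ePROs less tied to the sensor through pain, the stratum correlation can hold or rise. Agreement with the overall value does not show robustness, and disagreement does not show fragility. In a study of whether sensors can track treatment benefit, lower stratum values invite the reading that the sensor–ePRO link depends on response.

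The gate in Secondary Aim 3 has a related fault. Endpoints that pass do so partly because their week-12 estimate happened to be high. The same estimate is then the reference for week 18, so a stable effect looks as if it fades after supervised PT ends.

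**Working it through.** **Inputs from the documents.** Protocol 4.2 gives a planning effect of 0.40, published effects of 0.49 (pain) and 0.52 (function), two-sided alpha 0.05, 80% power, n = 52, 10% attrition and 60 enrolled. The plan gives no figure for the stratum correlations or the persistence contrast. Its sample size reproduces: a paired t-test at 0.40 needs 52 (power 0.808). For attrition, 52 × 1.1 = 57.2 gives the stated 57, and 52 / 0.9 = 57.8 would give 58. Expected completers are 60 × 0.9 = 54.

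**Assumed inputs.** All others: responder share, true correlations, baseline pain distribution, SD of change, and the correlation between week-12 and week-18 changes.

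**1. Split on WOMAC pain.** Let k be the SD of pain change in a stratum divided by the SD in everyone. With a linear relation,

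r(stratum) = r·k / √(r²k² + 1 − r²).

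For a normal change with the top 30% as responders, k² = 0.264 in responders and 0.493 in non-responders. At r = 0.50:
- responders: 0.50 × 0.514 / √(0.25 × 0.264 + 0.75) = 0.28
- non-responders: 0.50 × 0.702 / √(0.25 × 0.493 + 0.75) = 0.38

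| Responder share | True r | Responders | Non-responders |
|---|---|---|---|
| 30% | 0.30 | 0.16 | 0.22 |
| 30% | 0.50 | 0.28 | 0.38 |
| 30% | 0.70 | 0.45 | 0.57 |
| 50% | 0.30 | 0.19 | 0.19 |
| 50% | 0.50 | 0.33 | 0.33 |
| 50% | 0.70 | 0.51 | 0.51 |

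The actual rule is a percentage of baseline, so it was also simulated on a 0–20 pain score. There were 324 settings:
- baseline mean 8–10 and SD 2–4, limited to 1–20
- absolute change with SD 2.5–4 and correlation 0.2–0.6 with baseline, or percentage change with SD 25–45 points independent of baseline
- 30–50% responders
- follow-up score limited to 0–20 or not

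| True r | Responders | Non-responders |
|---|---|---|
| 0.30 | 0.15–0.30 | 0.18–0.27 |
| 0.50 | 0.26–0.50 (median 0.37) | 0.31–0.46 (median 0.39) |
| 0.70 | 0.42–0.70 | 0.48–0.66 |

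Here k was 0.47–1.01 in responders (median 0.69) and 0.56–0.89 in non-responders (median 0.73). One setting of 324 showed no attenuation in responders; non-responders were restricted in all. Spearman behaves alike: 0.46–0.49 overall becomes 0.25–0.48 and 0.28–0.44.

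**2. Other ePROs.** Let a be the sensor–pain correlation, b the ePRO–pain correlation, c the sensor–ePRO correlation and q = 1 − k². Then

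r(stratum) = (c − a·b·q) / √[(1 − a²q)(1 − b²q)].

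With c = 0.50 and the same k values:
- a 0.4–0.5, b 0.7–0.9: 0.27–0.50 in responders, 0.32–0.47 in non-responders
- a 0.2, b 0.5–0.9: 0.48–0.60
- a 0, b 0.3–0.7: 0.50–0.64

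**3. Precision.** At 30% responders the strata hold about 16 and 38 people. By Fisher's z, 0.28 at n = 16 has a 95% CI of −0.25 to 0.68. The all-participant 0.50 at n = 54 has 0.27 to 0.68.

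**4. Gate in Secondary Aim 3.** Take n = 54, equal true changes d at weeks 12 and 18, and correlation ρ between them. If m is the mean week-12 estimate among endpoints that pass, the contrast is biased by about −(1 − ρ)(m − d). At p<0.05:
- d = 0.20, m = 0.354: ρ = 0.5 gives −0.077 (simulated −0.075, 21% of m); ρ = 0.7 gives −0.046 (simulated −0.045, 13%)
- d = 0.40, m = 0.443: ρ = 0.5 gives −0.022 (5%); ρ = 0.7 gives about −0.013 (simulated −0.012, 3%)

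A p<0.01 gate, as an illustrative stand-in for Benjamini-Hochberg, raises the upper ends:

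| True d | Apparent loss, share of observed week-12 effect | False decline (nominal 2.5%) |
|---|---|---|
| 0.20 | 13–26% | about 5–10% |
| 0.30 | 7–16% | 3.7–6.1% |
| 0.40 | 3–9% | 2.9–3.9% |
| 0.49 | 1–4% | – |
| 0.52 | 1–3% | – |
| 0.60 | about 1% or less | – |

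At 0.40 the bias is 0.012–0.042 SD. The contrast's standard error, √[2(1 − ρ)/54], is 0.105–0.136. At 0.20 only 12–30% of endpoints pass the gate.

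**The case against.** The SAP only says it will estimate the correlation in each group. It claims no robustness, tests no difference between strata and attaches no decision. SAP 4.2 uses the same label for strata by PT attendance, so it may simply mean subgroup estimates. Whether the sensor tracks the ePRO among people with large pain relief is a fair question. WOMAC pain is one of ten ePROs, enters only if its week-12 change is significant, and the effect on the others runs both ways. The shift is also smaller than sampling error: 0.37 has a 95% CI of about −0.15 to 0.73 at n = 16 and −0.01 to 0.66 at n = 27. For Secondary Aim 3, asking about persistence only where an effect was shown is coherent and prespecified, and the bias is small at the planning effect.

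Much of this stands as a limit on scope: systematic attenuation is shown only for WOMAC pain and, when the sensor tracks pain, for close pain scores. It does not rescue the label. A subgroup defined on the outcome differs from one defined on attendance, because the definition itself changes the correlation. Imprecision adds to the difficulty of reading the strata and does not remove the bias.

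The simulations let baseline pain go down to 1, whereas Protocol 5.1 requires a minimum score on weight-bearing pain questions. If that is read as a floor of 3 on the 0–20 score (an assumption), the largest responder k falls from 1.01 to 0.95 and the single exception disappears, so the direction is slightly strengthened.

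**Conclusion.** The concern holds and should be corrected. As written, the responder and non-responder correlations are not a check on the overall result: for WOMAC pain a true 0.50 would typically show as about 0.37 and 0.39 through the split alone, and for other ePROs the strata can move either way. These sizes rest on assumed responder shares and pain distributions. That the split falls on a correlated outcome rests on the SAP's own definitions.

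The gate in Secondary Aim 3 is the lesser matter. Its bias is toward apparent loss and is material for weak endpoints, at true changes of about 0.2–0.3. It is small at 0.40 and negligible from about 0.6. It deserves attention because the 0.40 was set for WOMAC scores, and the sensor endpoints have no planning effect of their own.

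The consequence is confined to what may be concluded from Secondary Aims 1 and 3.

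**What to change.** **Secondary Aim 1.** Keep the all-participant correlation as the only inferential result in parts A and B. Either drop the stratum correlations or relabel them as descriptive, with the SD of WOMAC pain change in each stratum and a scatterplot marked by responder status. Do not call them sensitivity analyses. A comparison of mean sensor change between responders and non-responders is optional. The week-12 gate for these correlations can stay. Cost: wording in SAP 4.3 only.

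**Secondary Aim 3.** Report the week-18 change and the week-18 minus week-12 contrast, with 95% confidence intervals, for every sensor endpoint admitted to SAP 4.2 C and D and for all ten ePROs. Mark those with a significant week-12 change. State that a non-significant contrast is not read as persistence where no week-12 effect was shown. Cost: wording in SAP 4.3 and Protocol 7.2, aim 3, and a longer table. Counting each in-lab metric once, it has at most about 52 rows:
- in-lab: 14 gait + 4 sit-to-stand = 18
- at-home: 18 + 1 gait bouts + 5 Actigraph = 24
- ePROs: 10

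The Benjamini-Hochberg family grows only if the added contrasts are tested; giving them as estimates with intervals avoids that.
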